3.2 Secondary outcomes

We are also aiming to evaluate if FMT can possibly alter gut permeability through urinalysis and peripheral blood DNA bacteria. We also aim to evaluate treatment safety using the Expanded Disability Status Scale (EDSS) and MRI as surrogates for any paradoxical worsening in MS disease activity. We are monitoring adverse events to assess tolerability.

4. STUDY DESIGN

The proposed randomized, open label, with treat as usual control group, crossover phase II study will be conducted in 40 patients (n=20 per group) with the relapsing forms of multiple sclerosis according to the McDonald 2010 Criteria (Pollman 2011).

Patients will be randomized into 2 intervention groups. One will receive the FMT from baseline and for the first 6 months (early intervention group). On the other hand, the other group will be a control group during the first 6 months and will receive the FMT for the last 6 months of the study (Figure 1). The schedule of study procedures and evaluations for both groups is given in Tables 1 and 2. Patients will be screened for eligibility based on MS diagnosis and EDSS and if eligible then consented. All qualified patients will not be currently or recently treated with high dose steroids.

[figure not shown]

Figure 1. Study Design

At Visit 1, before FMT, patients will be evaluated for their vital signs, medical history and concomitant medications. Also before transplantation, patient's stool will be collected to study their microbial profile, blood analysis to evaluate cytokines levels as well as blood DNA bacteria and finally, urinalysis to assess gut permeability (baseline).

Stool samples for all microbiome analysis will be collected in the form of a used toilet paper packed in a black pouch and transferred in ambient conditions to the laboratory at the Lawson Health Research Institute at St. Joseph's Hospital and stored at -80 °C until the time of DNA extraction.

Peripheral blood will also be collected by standard technique venipuncture by a venipuncture certified and experienced RN. Cytokines levels will be assessed by Luminex in the Department of Microbiology and Immunology at the University of Western Ontario and blood DNA bacteria will be evaluated in St. Joseph Microbiology Laboratory.

For gut permeability patients will be instructed to drink lactulose solution and collect the urine throughout the night and first thing in the morning. A proper collecting bottle will be provided. Once the urine sample bottle reaches the laboratory at St. Joseph's Hospital, London, Ontario the total volume will be measured and an aliquot of 30ml total, 10mL in each sterile urine container (no other additives) will be separated and stored at -20C and sent on dry ice to [name] laboratory at Calgary, Alberta. All biological material will be transported according to biosafety regulations.

Patients will also undergo a contrast-enhanced brain MRI scan at Robarts Institute in London Ontario. Other baseline assessments (prior to the first dose of therapy) include an EDSS, pregnancy test (if applicable), and physical exam. Blood samples are also taken at this visit in order to establish a baseline for routine chemistry/hematology. After all this assessments FMT will be performed by a trained nurse via a rectal enema

Patients will return to the clinic for visit 4 weeks after the first FMT. Another stool sample to evaluate the microbial before the second FMT will be collected. Also peripheral blood samples for cytokines and blood bacterial DNA analysis. This same routine procedure will be

repeated at month 2, 3, 4 and 5 for the early intervention group and at month 6, 7, 8, 9, 10 and 11 for the late intervention group. Both groups will come to clinic at baseline and month 1 to 12 inclusive, even if they are not receiving FMT. During all visits, a stool sample, a cytokine sample and a blood DNA bacteria sample will be collected. It is worth mentioning that at 6 and 12 months another urine analysis will be done to evaluate gut permeability and MRI study at Robarts Institute, London, Ontario for safety assessment will be performed for both groups.

Another safety assessment in each visit after FMT is to review of any adverse events that may have occurred. All patients receiving at least 1 week of treatment will be eligible for analysis.

Table 1. Early Intervention Group Schedule

[figure not shown]
Study Months	Pre-Visit	Baseline	Month 1	Month 2	Month 3	Month 4	Month 5	Month 6	Month 7	Month 8	Month 9	Month 10	Month 11	Month 12
Visit Duration	1.5hours	1.5hours	1.5hours	1.5hours	1.5hours	1.5hours	1.5hours	45min	45min	45min	45min	45min	45min	45min
Informed Consent Form	X													
Fecal Transplantation		X	X	X	X	X	X							
Height		X												
Weight, Vital Signs		X	X	X	X	X	X	X	X	X	X	X	X	X
Stool Sample		X	X	X	X	X	X	X	X	X	X	X	X	X
Urine: Gut Permeability		X						X						X
Circulating Cytokine Levels and Blood DNA		X	X	X	X	X	X	X	X	X	X	X	X	X
MRI		X						X						X
Routine Hematology and Urinalysis		X	X	X	X	X	X	X	X	X	X	X	X	X
Physical Exam/ EDSS		X	X	X	X	X	X	X	X	X	X	X	X	X

Table 2. Late Intervention Group Schedule

Study Months	Pre-Visit	Baseline	Month 1	Month 2	Month 3	Month 4	Month 5	Month 6	Month 7	Month 8	Month 9	Month 10	Month 11	Month 12
Visit Duration	1.5 hours	45mins	45mins	45mins	45mins	45mins	45mins	1.5hours	1.5hours	1.5hours	1.5hours	1.5hours	1.5hours	1.5hours
Informed Consent Form	X													
Fecal Transplantation								X	X	X	X	X	X	
Height		X												
Weight, Vital Signs		X	X	X	X	X	X	X	X	X	X	X	X	X
Stool Sample		X	X	X	X	X	X	X	X	X	X	X	X	X
Urine: Gut Permeability		X						X						X
Circulating Cytokine Levels and Blood DNA		X	X	X	X	X	X	X	X	X	X	X	X	X
MRI		X						X						X
Routine Hematology and Urinalysis		X	X	X	X	X	X	X	X	X	X	X	X	X
Physical Exam / EDSS		X	X	X	X	X	X	X	X	X	X	X	X	X

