4.1 Rationale for FMT preparation

The processing of stool samples for FMT via enema is shown in the chart below. Sample processing shall be done in sterile conditions in Biosafety cabinet level⁶⁷.

FMT will be administered via rectal enema. Microflora will be studied from stool samples collected prior to administration of the FMT and will be stored at -80C. Before and after procedure the patients will be tested as per the chart given above. Data than shall be recorded periodically and analyzed for statistical significance.

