6.2.1 Screening, Enrolment and Baseline

An informed consent form must be signed prior to initiating any procedures or evaluations for the purpose of the study (**Appendix B**). After the informed consent form has been signed patients will be randomized to receive FMT for the first 6 months of the study or to be a standard per treatment control group that will received treatment at the last 6 months of the study.

The following evaluations at baseline visit and prior to FMT will be performed in both groups:

- Medical history;
- Vital signs (including pulse, respiration rate, blood pressure and temperature);
- Physical Exam (including weight in kg);
- Concomitant medications;
- Dietary history;

- Expanded Disability Status Score (EDSS);
- Blood samples will be taken for haematology (including haemoglobin, red blood cell count, white blood cell count, differential and platelets);
- Blood samples will be taken for serum chemistry (sodium, potassium, chloride, uric acid, creatinine, blood urea nitrogen, total protein, calcium, albumin, total bilirubin, AST, ALT, alkaline phosphatase, glucose);
- Blood sample for multiplex cytokine profiling (includes pro-inflammatory (IL-6, IL-15, IL-17, GM-CSF, TNF α) and anti-inflammatory (IL-4, IL-10 and IL-14) cytokines).
- Clean catch, mid-stream urine for urinalysis and micro analysis (including pH, protein, glucose, ketones, nitrites, leukocyte esterase, RBCs, WBCs) and gut permeability;
- Blood sample for blood bacterial DNA
- Head MRI as baseline

After evaluation, the FMT via rectal enema will be performed by a RN in each visit.

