6.2.2 Subsequent visits

On all subsequent visits, prior to FMT the following evaluations will be performed:

- Physical examination
- Rapid (urine) pregnancy test for women of childbearing potential;
- Vital signs (including pulse, respiration rate, blood pressure and temperature);
- Concomitant medications;
- EDSS;
- Blood samples will be taken for haematology (including haemoglobin, red blood cell count, white blood cell count, differential and platelets);
- Blood samples will be taken for serum chemistry (including: sodium, potassium, chloride, uric acid, creatinine, blood urea nitrogen, total protein, calcium, albumin, total bilirubin, AST, ALT, alkaline phosphatase, glucose);
- Clean catch, mid-stream urine for urinalysis and micro analysis (including pH, protein, glucose, ketones, nitrites, leukocyte esterase, RBCs, WBCs,);
- Blood sample for blood bacterial DNA
- Blood sample for multiplex cytokine profiling (includes pro-inflammatory (IL-6, IL-15, IL-17, GM-CSF, TNF α) and anti-inflammatory (IL-4, IL-10 and IL-14) cytokines).

After evaluation, the FMT via rectal enema will be performed by a RN in each visit.

At baseline, 6 and 12 months a head MRI will be performed. At these time points urine will be also collected to perform gut permeability analysis.

At any time during the study, if a patient has experienced an adverse event then they may be asked to return to the clinic for an unscheduled visit. Patients with adverse events will be followed to resolution.

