9.4 Safety Analysis

Adverse events will be coded using MedDRA dictionary. Incidence of adverse events by the severity, relationship to treatment, and outcome will be provided. Narratives of all serious adverse events and events causing death will be included. Laboratory parameters, vital signs and other safety parameters will be documented with the use of descriptive statistics.

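### Adverse-event questioning is not scheduled equally in the untreated months, and no AE summary by randomised group or period is planned

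*Combined protocol and SAP*

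**What the plan says.** Safety and tolerability of FMT are the secondary objectives (synopsis). Section 3.2 names EDSS and MRI as the safety surrogates and AE monitoring as the measure of tolerability.

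On collection, section 4 says: "Another safety assessment in each visit after FMT is to review of any adverse events that may have occurred". This is the only place where an AE review is attached to a visit. Tables 1 and 2 have no AE row, and the evaluation lists in 6.2.1 and 6.2.2 have no AE item. Between visits, 6.2.2 adds that "if a patient has experienced an adverse event then they may be asked to return to the clinic for an unscheduled visit". Attendance is the same in both groups: "Both groups will come to clinic at baseline and month 1 to 12 inclusive, even if they are not receiving FMT".

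On what counts, the synopsis and 8.2.2 require every AE in the study to be recorded whatever its cause, and the lead sentence of 8.2.1 is equally broad. The two bullets beneath it, however, are tied to the start or course of study treatment, which late-group patients do not begin until month 6.

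On analysis, section 9.4 says: "Incidence of adverse events by the severity, relationship to treatment, and outcome will be provided". Section 9.7 bases all analyses and listings on patients who received one week of study treatment.

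**The concern.** The late group's months 0 to 6 are the trial's only concurrent, randomised, untreated follow-up. To serve as a control for AEs, that period needs the same question asked at the same times as in the early group, and a table that separates the groups. The plan as written secures neither.

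A duty to record is not a schedule for asking. If one group is asked every month and the other relies on spontaneous report, AE counts can differ for reasons unrelated to FMT. If the summary is then pooled over groups and periods, tolerability rests on the investigator's relatedness judgement, made open label. The symptoms that section 2.7 lists for FMT (abdominal pain, diarrhoea, flatulence, fatigue and the like) are non-specific, so background matters. Questions not asked in the control months cannot be recovered reliably later.

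**Working it through.** **The plan's own figure.** The documents give no AE rate or safety sample size for this trial. Section 2.7 cites an FMT-attributable AE rate for lower-gastrointestinal routes: 76/430 = 0.1767, or 17.7%. It reproduces.

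**Visits covered by the section 4 sentence.** Inputs: 20 patients per group and monthly visits 1 to 12 (synopsis, Tables 1 and 2); first FMT at baseline in the early group and at month 6 in the late group. Follow-up visits: 12 × 40 = 480.

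- *Reading A: visits later than a patient's first FMT.* Early group, months 1 to 12: 12 × 20 = 240. Late group, months 7 to 12: 6 × 20 = 120. Late group, months 1 to 6, not covered: 6 × 20 = 120, which is 120/480 = 25% of follow-up visits and all of the concurrent untreated follow-up. The month 6 visit counts as untreated because 6.2.2 places its evaluations before the enema ("On all subsequent visits, prior to FMT the following evaluations will be performed").
- *Reading B: within a visit, after the enema.* Early group, baseline to month 5: 6 × 20 = 120. Late group: no review before its first enema at month 6.

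On either reading the early group is asked during the first six months and the untreated late group is not.

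**How much background could matter.** Assume that a share b of patients have a background AE over six months (b is not in the documents; 10%, 20% and 30% are shown), independent of FMT-attributable events at 17.7%. Section 2.7 gives no follow-up time for that rate, so it is illustrative only. Then:

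- early-group proportion with any AE: p = 1 − (1 − 0.1767)(1 − b)
- expected patients: 20p; from background alone: 20b; share: b/p
- difference between groups: p − b
- approximate 95% half-width: 1.96 × √[b(1 − b)/20 + p(1 − p)/20]

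| b | p | 20p | 20b | b/p | p − b | half-width |
|---|---|---|---|---|---|---|
| 10% | 25.9% | 5.2 | 2 | 39% | 15.9 points | 23.3 points |
| 20% | 34.1% | 6.8 | 4 | 59% | 14.1 points | 27.2 points |
| 30% | 42.4% | 8.5 | 6 | 71% | 12.4 points | 29.5 points |

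A pooled table cannot show the background share. A table by group can describe it, but every half-width exceeds its difference, so 20 v 20 supports description and not a test.

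**Section 9.7.** No number is attached. The documents do not say how many late-group patients might leave before month 6, and the 90% target in 5.4 covers FMT and all follow-up together, so it cannot supply one.

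**The case against.** The strongest reply is that control-period AEs are already covered. The synopsis and 8.2.2 require all AEs to be recorded. Section 8.2.1 identifies an AE from physical examination, laboratory results, or signs and symptoms; examination, vital signs, haematology and urinalysis are scheduled monthly in both groups, including the late group's untreated months. The section 4 sentence may simply be loose wording in a passage about both groups. The study is also a 40-patient proof of concept, too small for a formal AE comparison.

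Much of this stands, and it rules out several stronger readings that a reader might infer:

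- *Control-month AEs are excluded.* They are not. What is unequal is the scheduled questioning, which matters most for symptoms that examinations and laboratory tests do not reveal. No under-count can be estimated from the documents.
- *The control is unused for safety altogether.* EDSS at every visit and MRI at baseline, 6 and 12 months are collected identically in both groups. It remains true that no between-group comparison of them is specified, and the MRI rule in the synopsis compares each scan with the patient's previous one.
- *Section 9.7 removes untreated late-group patients.* Only if study treatment means FMT. The section says who is included and does not expressly exclude anyone else.
- *Nothing is checked after the enema.* Sections 6.2.1 and 6.2.2 do list vital signs before FMT, but 4.1 says: "Before and after procedure the patients will be tested as per the chart given above". Tables 1 and 2 give one mark per visit without timing within the visit, so the documents do not settle this either way.

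The reply does not supply an AE question at the late group's months 1 to 6, or any AE summary by group or period.

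**Conclusion.** The point holds as a matter of ascertainment and reporting. Taken as written, the plan schedules AE questioning for the early group but not the untreated late group in months 1 to 6 (120 visits against none under reading A), and it plans no AE summary that would use the randomised comparison. The consequence for tolerability is a possible bias of unknown size plus reliance on open-label attribution. The 39% to 71% range depends on the assumed background rates, on independence, and on carrying the cited 17.7% over to this population. The part concerning 9.7 depends on how study treatment is read. None of this touches the cytokine objective. The change is worth making because it is cheap and the missing answers could not be collected afterwards.

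**What to change.** 1. **Section 4 and Tables 1 and 2.** Replace the AE sentence with: at every visit from month 1 to month 12 in both groups, whether or not FMT is given, the same AE question is asked; AEs are counted from randomisation. Add an AE row to both tables. At month 6, ask the late group before its first enema. State that counting from randomisation takes precedence over the treatment-based bullets in 8.2.1.
2. **Section 9.4.** Add one descriptive table of patients with at least one AE, overall and by severity, from randomisation to the month 6 visit (before the late group's first FMT). Compare the early group with the untreated late group in all randomised patients, with exact 95% confidence intervals and no test. Exempt this table from section 9.7.
3. **Optional.** Reword 4.1 to say what is measured after the enema, for instance one repeat of the existing vital-sign set before the patient leaves.

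**Cost.** One table and a few sentences; no new visit or laboratory test. Assuming 1 to 2 minutes per AE question, 480 visits take 480 to 960 minutes, or 8 to 16 hours over the study at most, since part of this is already planned. Reported AE counts will rise, recall still spans about four weeks, and open-label reporting may still differ by group.

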4.1 Rationale for FMT preparation

The processing of stool samples for FMT via enema is shown in the chart below. Sample processing shall be done in sterile conditions in Biosafety cabinet level⁶⁷.

FMT will be administered via rectal enema. Microflora will be studied from stool samples collected prior to administration of the FMT and will be stored at -80C. Before and after procedure the patients will be tested as per the chart given above. Data than shall be recorded periodically and analyzed for statistical significance.

4.2 Duration of therapy and study

Patients will be screened prior to starting treatment with FMT and randomized between 2 groups. One, early intervention group, will receive FMT for the first 6 months and the other will be a control group treated as standard only. After 6 months, the early intervention will not receive the transplantation anymore and the control group will receive FMT for the remaining 6 months. Study drug will be administered for a period of 6 months for each group total.

Patients may withdraw consent at any time. Study drug may be discontinued at any time by the investigator if doing so is deemed to be in the best interest of the patient. However, the patient should be encouraged to continue in the study for safety follow-up.

4.3 Study Termination

The Investigator reserves the right to terminate this study at any time. In terminating the study, the Investigator will ensure that adequate consideration is given to the protection of the patients' safety and interests.

5. SELECTION AND WITHDRAWAL OF PATIENTS

5.1 Donor Screening Criteria

Donors will be selected according to a standard protocol (appendix A). This is included in this protocol for information only. Donors will have been already selected and material will be already processed by [name] lab at St Joseph's Hospital, London, Ontario, as per their standard of care.

5.2 Patient selection

5.2.1 Patient Inclusion criteria

- Have a confirmed diagnosis of relapsing (relapsing-remitting or secondary progressive) MS defined by the 2010 Revised McDonald Criteria for the Diagnosis of Multiple Sclerosis¹. Any disease duration will be accepted.
- Have a baseline EDSS of = or <7.0
- Older than 18 years of age.
- Be able to attend all clinic appointments without interruption
- Patients must be able to understand English sufficiently well to understand and comply with the clinic and medication schedules and procedures.
- Be willing and able to give written informed consent

- Negative blood pregnancy test at screening

5.2.2 Patient Exclusion criteria

- Not meeting all of the above inclusion criteria
- Pregnancy or breastfeeding
- Current or recent [in the last 90 days] exposure to high dose corticosteroids
- Ongoing use of antibiotics
- Presence of a chronic intestinal disease e.g. Celiac, malabsorption, Colonic tumor
- Inability to provide informed written consent.
- Immunosuppression from transplantation, HIV, Cancer chemotherapy or ongoing use of any immunosuppressive agents.
- Concomitant inflammatory diseases
- Any contra-indications for MRI. Participants are to be screened by a CMRTO certified MRI Technologist in order to determine the MRI compatibility or exclusion of implantable/external devices according to the manufacturer’s safety guidelines. The devices include cerebral aneurysm clips, neuro-stimulator, mechanical heart valves, cardiac stents, IUDs, vena cava filters, shunts, embolization coils, cochlear implants, non-removable prosthesis/artificial limbs. Contraindications are pacemaker of defibrillator, shrapnel/metallic fragments, previous brain surgery, seizure, severe claustrophobia, weight or body index that will prevent a successful MRI study.

5.3 Recruitment of trial patients.

Successful recruitment will be 3-6 patients per month on average. The goal is a total recruitment of 20 patients/12 months given the high numbers of competing studies, missed patients, consent failure rates and the refusal of an FMT strategy. We expect to monitor success with recruitment throughout the study and make revisions to recruitment procedures and eligibility criteria as necessary.

5.3.1 Recruitment of Healthy Volunteers.

Advertising will be posted throughout campus and hospitals in London announcing this study and calling for self-reported healthy individuals 18 y/o and older to participate in this study as a “control group”. We will recruit up to 10 [ten] volunteers. Participation will entail a single visit to the clinic for proper written informed consent prior to obtaining 1 tube, 5 ml of blood via standard of care venipuncture in one arm administered by a qualified registered nurse or lab technician. The tube with blood will be labeled with a study ID and sent to [name] lab for analysis in a completely de-identified fashion. This “control group” will not have any further participation in this study.

5.4 Adherence to protocol.

Successful adherence will be defined as =90% of patients progressing to FMT and all follow-up. Preliminary estimates of non-administration of the trial intervention are needed, along with strategies that maximize exposure to the intervention.

